## 5. TREATMENT PLAN

### 5.1 Agent Administration (Amended)

Treatment will be administered on an outpatient basis. Reported adverse events and potential risks are described in Section 7. Appropriate dose modifications are described in Section 6. No investigational or commercial agents or therapies other than those described below may be administered with the intent to treat the patient's malignancy.

*Week 0:*

- *Talimogene laherparepvec up to 4 mL of 1x10^6 PFU/mL*

*Week 1:*

- *5-Fluorouracil (5-FU) 400 mg / m^2 IV bolus followed by 5-Fluorouracil (5-FU) 2400 mg / m^2 continuous IV infusion over 46 hours*
- *Leucovorin 400 mg /m^2 IV bolus*
- *Oxaliplatin 85 mg/m^2 IV over 2 hours*

*Week 3:*

- *Talimogene laherparepvec up to 4 mL of 1x10^7 PFU/mL Or 1x10^8 PFU/mL based on assigned dose level*
- *5-Fluorouracil (5-FU) 400 mg / m^2 IV bolus followed by 5-Fluorouracil (5-FU) 2400 mg / m^2 continuous IV infusion over 46 hours*
- *Leucovorin 400 mg /m^2 IV bolus*
- *Oxaliplatin 85 mg/m^2 IV over 2 hours*

*Week 5:*

- *Talimogene laherparepvec up to 4 mL of 1x10^7 PFU/mL Or 1x10^8 PFU/mL based on assigned dose level*
- *5-Fluorouracil (5-FU) 400 mg / m^2 IV bolus followed by 5-Fluorouracil (5-FU) 2400 mg / m^2 continuous IV infusion over 46 hours*
- *Leucovorin 400 mg /m^2 IV bolus*
- *Oxaliplatin 85 mg/m^2 IV over 2 hours*

*Week 7:*

- *Talimogene laherparepvec up to 4 mL of  $1 \times 10^7$  PFU/mL Or  $1 \times 10^8$  PFU/mL based on assigned dose level*
- *5-Fluorouracil (5-FU) 400 mg /  $m^2$  IV bolus followed by 5-Fluorouracil (5-FU) 2400 mg /  $m^2$  continuous IV infusion over 46 hours*
- *Leucovorin 400 mg /  $m^2$  IV bolus*
- *Oxaliplatin 85 mg/ $m^2$  IV over 2 hours*

*Weeks 9 / 10:*

- *Radiation 25 Gy over 5 fractions*

*Weeks 12 / 13:*

- *5-Fluorouracil (5-FU) 400 mg /  $m^2$  IV bolus followed by 5-Fluorouracil (5-FU) 2400 mg /  $m^2$  continuous IV infusion over 46 hours*
- *Leucovorin 400 mg /  $m^2$  IV bolus*
- *Oxaliplatin 85 mg/ $m^2$  IV over 2 hours*

*Weeks 14 / 15:*

- *5-Fluorouracil (5-FU) 400 mg /  $m^2$  IV bolus followed by 5-Fluorouracil (5-FU) 2400 mg /  $m^2$  continuous IV infusion over 46 hours*
- *Leucovorin 400 mg /  $m^2$  IV bolus*
- *Oxaliplatin 85 mg/ $m^2$  IV over 2 hours*

*Weeks 16 / 17:*

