## 5.2 **Definition of Dose-Limiting Toxicity**

Dose limiting toxicities (DLTs) will be captured until completion of FOLFOX chemotherapy (weeks 18/19) and will be graded according to the CTCAE ver 5. DLTs will be defined as clinically significant grade 3 or 4 toxicities possibly or probably related to study treatment. The following AEs will not be considered DLTs:

- any grade of alopecia,
- grade 3 arthralgia or myalgia,
- brief (< 1 week) grade 3 fatigue,
- grade 3 fever
- grade 3 diarrhea or vomiting responding to supportive care.
- grade 3 radiation dermatitis

All patients who have received at least one dose of the study regimen are evaluable for toxicities; for dose escalation decisions, patients should have completed  $\geq 80\%$  of the planned chemotherapy and radiation doses unless the reason for discontinuation is an AE that qualifies for DLT.

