### **AEs that are considered “Dose Limiting” for talimogene laherparepvec**

- 1) Herpetic events that should be considered DLTs:
  - Serious herpetic events such as herpetic encephalitis, encephalomyelitis or disseminated herpetic infection

- Any herpetic events confirmed due to talimogene laherparepvec that require treatment with acyclovir or similar anti-viral agent. Talimogene laherparepvec treatment should be held if systemic acyclovir or other anti-viral is indicated. If ongoing anti-viral treatment is required, talimogene laherparepvec treatment should be permanently discontinued
  - \* Herpetic events due to wild-type HSV-1 or wild-type HSV-2 which require acyclovir and are not due to talimogene laherparepvec (as confirmed by PCR testing) should not be considered as DLTs caused by talimogene laherparepvec.

2) DLT will also be defined as any of the following talimogene laherparepvec-related toxicity:

- Grade 2 or greater immune-mediated AEs.
- Grade 2 or greater allergic reactions.
- Any grade plasmacytoma
- Any other grade 3 or greater hematologic or non-hematologic toxicity, with the exceptions of:
  - any grade of alopecia,
  - grade 3 arthralgia or myalgia,
  - brief (< 1 week) grade 3 fatigue,
  - grade 3 fever,
  - grade 3 diarrhea or vomiting responding to supportive care.

For other study treatments, DLT will be defined as clinically significant (ie excluding any grade alopecia, grade 3 arthralgia or myalgia, < 1 week grade 3 fatigue, grade 3 diarrhea, nausea, vomiting responding to supportive care), grade 3 or 4 toxicities possibly or probably related to study treatment or AEs.

Management and dose modifications associated with the above adverse events are outlined in Section 6.

Dose escalation will proceed within each cohort according to the following scheme. Dose-limiting toxicity (DLT) is defined above.

Number of Patients with DLT at a Given Dose Level	Escalation Decision Rule
0 out of 3	Enter 3 patients at the next dose level.
≥2	Dose escalation will be stopped. This dose level will be declared the maximally administered dose (highest dose administered). Three (3) additional patients will be entered at the next lowest dose level if only 3 patients were treated previously at that dose.

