1 out of 3	Enter at least 3 more patients at this dose level. 

• If 0 of these 3 patients experience DLT, proceed to the next dose level.

• If 1 or more of this group suffer DLT, then dose escalation is stopped, and this dose is declared the maximally administered dose. Three (3) additional patients will be entered at the next lowest dose level if only 3 patients were treated previously at that dose.

≤1 out of 6 at highest dose level	This is generally the maximum tolerated dose, MTD. At least 6 patients must be entered at the MTD.

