### **Dose Reductions/delay:**

- Dose reductions with regards to changes in the concentrations of talimogene laherparepvec are not permitted. However, patients may require a reduction in the volume injected due to a disease response (defined in dosing section) or due to local toxicity at the injection site.
- If talimogene laherparepvec treatment was delayed due to AEs or other reasons by >1 week, that dose will be deemed to have been missed and the subject will proceed to the next scheduled treatment visit.
- If DLTs occur, talimogene laherparepvec administration should be delayed until the DLT has resolved to at least CTCAE version 5.0 Grade 1. (AEs less than DLT may also require talimogene laherparepvec dose delay. See instructions in Table below)
- If talimogene laherparepvec dosing is delayed by more than 4 weeks (approximately 6 weeks from the previous dose) due to treatment related AEs, talimogene laherparepvec should be permanently discontinued.
- If talimogene laherparepvec dosing is delayed by more than 4 weeks (approximately 6 weeks from the previous dose) for reasons other than treatment-related toxicity, the case

must be reviewed by the sponsor of the study (CTEP) to determine if the subject can resume talimogene laherparepvec therapy.

Treatment delays and discontinuation due to Specific AEs		
Condition	Grade	talimogene laherparepvec modification
• Injection site reactions		Volume of talimogene laherparepvec injection may be adjusted and should be held based on the degree of local toxicities
• Active herpetic cutaneous or mucosal lesions, herpes labialis, or active dermatosis in the region of the injected tumor (s)		Mild: continue talimogene laherparepvec; If requiring systemic acyclovir or similar anti-viral agents: Hold talimogene laherparepvec.
• Serious herpetic events such as herpetic encephalitis, encephalomyelitis or disseminated herpetic infection	Any grade	Discontinue talimogene laherparepvec
• Any condition requiring corticosteroid dosing of >10 mg prednisone daily (or equivalent) and/or other immunosuppressive medication for related toxicities	N/A	Hold talimogene laherparepvec dosing until corticosteroid dose has decreased to <10 mg prednisone daily (or equivalent) and the other immunosuppressive medication has been stopped.
• Plasmacytoma	Any grade	Permanently discontinue talimogene laherparepvec

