• Immune-mediated AEs (These may include pauci-immune glomerulonephritis, vasculitis, and pneumonitis, but may involve any organ system)	Grade 2 or greater	Hold talimogene laherparepvec (with the exception of vitiligo). If delay is > 4 weeks, discontinue talimogene laherparepvec
• Allergic reactions, or urticaria	Grade 2 or greater	Hold talimogene laherparepvec. If delay is > 4 weeks, permanently discontinue talimogene laherparepvec

 
• Other talimogene laherparepvec related grade 3+ AEs or intolerable grade 2 AEs (Except brief grade 3 fever, fatigue, pain, or nausea/vomiting responding to supportive care)
 
		
Hold talimogene laherparepvec until AE is grade 0-1.
 
 
• If delay is > 4 weeks, discontinue talimogene laherparepvec
 
• If the AE was grade 4, decision to resume talimogene laherparepvec upon recovery should be reviewed with the sponsor (CTEP)
 

--	--	---

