## 13. STATISTICAL CONSIDERATIONS

### 13.1 Study Design/Endpoints

Primary Endpoint:

To determine the dose limiting toxicities and maximum tolerated dose of TALIMOGENE LAHERPAREPVEC in combination with chemotherapy and radiation in rectal cancer

Study Design:

Chemoradiation will be at current standard of care doses i.e. 50.4 Gy over 28 fractions in combination with capecitabine 825 mg/m^2 po bid, days of radiation only (M-F). TALIMOGENE LAHERPAREPVEC will be escalated in 2 dose levels (PFU /ml) as indicated below using a standard 3 + 3 design.

- Talimogene laherparepvec will be administered via endoscopy by a qualified physician for a total of 4 doses at the following time points: a) week 1 prior to initiation of FOLFOX chemotherapy b) weeks 2-4 during FOLFOX chemotherapy c) week 6 d) week 8-9 during chemoradiation
- The first cohort of 3 patients will be treated at dose level 1.
- The next cohort of patients will not be treated until toxicity has been evaluated in the current cohort of patients.
- The algorithm is as follows: (1) If 0 out of 3 patients experiences dose-limiting toxicity (DLT), the next cohort of 3 patients will be treated at the next higher dose level. (2) If 1 out of 3 patients develops DLT, additional 3 patients will be treated at the same dose level. If no more DLT develops at the dose, i.e. 1 out of a total of 6 patients develops DLT, the dose escalation continues to next higher level for a cohort of 3 patients. (3) At any given dose, if more than 1 out of 3 patients or 6 patients experience DLT, the dose level exceeds the MTD and 3 patients will be treated at the next lower dose level if there are less than 6 patients already treated at that dose. If this is the lowest dose level tested, the trial will be terminated and MTD is not found. Following the above algorithm, MTD is defined as the highest dose level in which 6 patients have been treated with at most 1 instance of DLT

Dose level	TALIMOGENE LAHERPAREPVEC Dose (PFU/ml)	Capecitabine (mg/m  po bid on days of radiation)	Radiation
1	10  , 10  , 10  , 10 	825	50.4 gray in 28 fractions
2	10  , 10  , 10  , 10 	825	50.4 gray in 28 fractions

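### The evaluability rule for dose decisions sets a minimum for chemotherapy and radiation but none for talimogene, the only agent being escalated

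*Combined protocol and SAP*

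**What the plan says.** Section 5.2 separates general toxicity evaluability (one dose of the regimen) from evaluability for dose escalation. For the latter a patient needs at least 80% "of the planned chemotherapy and radiation doses unless the reason for discontinuation is an AE that qualifies for DLT". Talimogene is not mentioned. The primary objective in 1.1 names talimogene apart from chemotherapy and radiation, so the phrase cannot be read to include it.

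Section 5.1 gives the week 0 injection at 10^6 PFU/mL to everyone. Only at weeks 3, 5 and 7 is the concentration 10^7 or 10^8 "PFU/mL based on assigned dose level".

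The escalation table in 5.2 says of at most 1 DLT in 6 at the highest level: "This is generally the maximum tolerated dose, MTD. At least 6 patients must be entered at the MTD". Section 13.1 agrees: "MTD is defined as the highest dose level in which 6 patients have been treated with at most 1 instance of DLT". Neither says how much talimogene makes a patient treated at a level.

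Level-specific talimogene can be lost without a DLT:
- Under Dose Reductions/delay in 6.1, an injection is skipped if "delayed due to AEs or other reasons by >1 week, that dose will be deemed to have been missed".
- The table there holds talimogene for "Other talimogene laherparepvec related grade 3+ AEs or intolerable grade 2 AEs". Grade 2 events other than immune-mediated or allergic ones are generally not DLTs.
- Talimogene is held when systemic antivirals are needed, yet 5.2 excludes from the DLTs "Herpetic events due to wild-type HSV-1 or wild-type HSV-2 which require acyclovir and are not due to talimogene laherparepvec".
- Short of a missed injection, "patients may require a reduction in the volume injected due to a disease response (defined in dosing section) or due to local toxicity".

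**The concern.** The primary objective is the MTD of talimogene in this combination. A 3+3 design reads the absence of a DLT as evidence that the assigned dose is tolerated, which requires that the patient received that dose. Here a patient can miss every level 2 injection, complete FOLFOX and radiation without a DLT, and count as tolerating level 2. Any such miscount favours declaring level 2 safe, and nothing in the MTD rule would reveal it. The sponsor review in 13.1 is tied to starting new dose levels. Level 2 is the last one, so that review does not cover declaring it the MTD.

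**Working it through.** **The plan's own figures.** In 13.1, the chance of at least one DLT in 15 is 1 − 0.833^15 = 93.5% and 1 − 0.70^15 = 99.5%; both match. For the 3+3 table, a level passes with 0/3, or with 1/3 then 0/3: (1−p)^3 + 3p(1−p)^2 × (1−p)^3.
- Scenario 1 (0.10, 0.17): 0.906 × 0.773 = 70.0%, stated 70%.
- Scenario 2 (0.10, 0.25): 0.906 × 0.600 = 54.4%, stated 57%. The difference is compatible with simulation error if about 1,000 runs were used (assumed; no number is given).

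These figures give every level 2 patient the level 2 DLT rate. The evaluability rule does not secure that premise.

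**Exposure of a patient who counts.** Planned level 2 PFU per mL injected, at constant volume: 10^6 + 3 × 10^8 = 3.01 × 10^8.
- Week 0 only: 0.01/3.01 = 0.3%.
- Week 0 plus one level-specific injection: 1.01/3.01 = 34%.
- Week 0 plus two: 2.01/3.01 = 67%.

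All three patients meet the 5.2 rule if they complete 80% of FOLFOX and radiation. The full level 1 plan is 10^6 + 3 × 10^7 = 3.1 × 10^7 per mL, so one 10^8 injection plus week 0 already gives 1.01 × 10^8 / 3.1 × 10^7 = 3.3 times the level 1 total.

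**Effect on the MTD decision.** Suppose u of the 6 patients have the level 1 DLT rate a, and 6 − u have the level 2 rate b. Then

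P(0 DLT) = (1−a)^u (1−b)^(6−u)

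P(1 DLT) = P(0 DLT) × [u·a/(1−a) + (6−u)·b/(1−b)]

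Scenario 2 (a = 0.10, b = 0.25):
- u = 0: 0.178 + 0.356 = 0.534
- u = 1: 0.214 + 0.380 = 0.593
- u = 2: 0.256 + 0.399 = 0.655

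Scenario 1 (a = 0.10, b = 0.17) gives 0.729, 0.757 and 0.785.

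Because of the 3.3-fold figure, rate a is plausible mainly for patients who miss all three level-specific injections. These are upper illustrations.

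**Whether the RP2D rule would catch it.** Sections 5.3 and 13.1 require at least 80% of patients to receive at least 80% of planned treatment doses, without saying whether this is per agent. If pooled, the plan has 4 talimogene + 8 FOLFOX + 5 fractions = 17 doses, or 13 with radiation as one course, or 12 for drugs alone. A patient missing two level-specific injections passes every way: 15/17 = 88%, 11/13 = 85%, 10/12 = 83%. One missing all three passes only if fractions count: 14/17 = 82%, against 10/13 = 77% and 9/12 = 75%.

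**The case against.** Several safeguards exist. Section 12.1 requires Principal Investigator sign-off on escalation, expansion and de-escalation decisions, and going from 6 to 15 patients at level 2 is an expansion. It also gives the investigator and statistician constant data access and sets at least monthly calls with CTEP. Sections 5.3 and 13.1 add real-time safety monitoring and stop enrolment if one third or more of the patients at the MTD have DLTs. A reader might infer that only the CTEP calls stand between six patients and the MTD, or that the dose is settled on six; the documents support neither. What remains is that no safeguard sets an exposure criterion, and under-exposed patients would also sit in the denominator of the one-third rule.

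The routes are narrower than the hold table alone suggests. Besides grade 3 or higher talimogene-related toxicity (with listed exceptions), 5.2 counts as DLTs grade 2 or higher immune-mediated and allergic events, any plasmacytoma, serious herpetic events, and talimogene-confirmed herpes needing antivirals. Exclusions 3.2.9 and 3.2.10 make wild-type herpes less likely. This stands. It leaves delays for other reasons, other intolerable grade 2 events and new wild-type herpes.

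Frequency may be low. Section 2.4 reports no dose interruptions at level 1 and 4% discontinuation for AEs in the phase III melanoma trial. If 4% of patients were under-exposed, the average scenario 2 rate would be 0.96 × 0.25 + 0.04 × 0.10 = 0.244, and the chance of at most 1 DLT in 6 would be 54.8% rather than 53.4%. That trial was monotherapy and the figure excludes temporary holds, so it is only indicative, but it argues against assuming a large effect.

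Finally, keeping toxicity-driven shortfalls in the count leaves their effect on the 1-in-6 rule unchanged. That is accepted deliberately: replacing those patients would discard evidence of intolerance.

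**Conclusion.** The gap is real: followed as written, the rule can count a patient who received no level 2 injection as tolerating level 2. Its consequence is possible rather than expected. The documents give no level 2 delivery data, and the rise from 53% to 59% or 66% rests on the scenario 2 rates and on under-exposed patients having the level 1 DLT rate.

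A reader might go further, for example to three under-exposed patients of six, where the same sum gives 72%, or to applying the level 1 rate to anyone who missed an injection. Nothing in the documents suggests that half a cohort would lose all level 2 injections, and the 3.3-fold PFU figure argues against the second step. Nor do the documents show that the level 2 MTD would be wrong.

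This is a cheap improvement to the plan's wording.

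**What to change.** 1. In 5.2, for patients without a DLT, also require at least 2 of the 3 level-specific talimogene injections at the assigned concentration to count in escalation and MTD decisions. Replace patients who fall short for reasons unrelated to toxicity, within the cap of 21 in 13.2. Keep toxicity-driven shortfalls in the count and flag them at the 12.1 sign-off before the MTD is declared.
2. In 5.3 and 13.1, state that the RP2D delivery rule is assessed for talimogene separately, not pooled with FOLFOX and radiation, at a threshold consistent with 5.2. Do not introduce an 80% PFU criterion: 2 of 3 injections is 67% of PFU, so a patient adequate for the MTD would fail for the RP2D.
3. In 13.4, tabulate delivered against assigned talimogene, with the reason for any shortfall, beside each patient's DLT status. Volume set by the tumour-size table in 8.1 is normal dosing, not a shortfall.

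**Cost.** Wording in four sections, plus injected volume and reason on the CRF if not already collected. Feasibility may look less favourable than under a pooled reading. If level 2 is the MTD, 3 + 15 = 18 patients leaves 3 places for replacement. If level 2 fails, 3 + (3 to 6) + 15 = 21 to 24, assuming the original level 1 patients, who had different radiation, do not count toward the 15. That leaves no places, so under-exposed patients could only be flagged.

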### 5.3 **Dose Expansion Cohorts:**

A total of 15 patients will be treated at the MTD (including the 6 from dose expansion) to assess safety and feasibility of this dose level. The MTD will be deemed to be recommended phase II dose (RP2D) if  $\geq 80\%$  of the patients are able to receive  $\geq 80\%$  of the planned treatment doses. If  $\geq 1/3$  of all patients at this dose experience DLTs, enrollment will be stopped and the Principal Investigator will discuss with all study investigators and with CTEP whether further addition of patients is needed to re-assess the RP2D. Monitoring of all safety and toxicity data is done by the Principal Investigator and the Corresponding Organization on a real-time basis as data are entered into Medidata Rave using the Web Reporting Module.

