Grade 3	Hold* until < Grade 2. Resume at one dose level lower, if indicated.	Hold* until < Grade 2. Resume at one dose level lower, if indicated. **

Grade 4	Off protocol therapy	Off protocol therapy
*Patients requiring a delay of >2 weeks should go off protocol therapy.		
Recommended management: ondansetron 4-8 mg ODT or by mouth every 6-8 hours and / or prochlorperazine 5-10 mg po every 4-6 hours or other anti-emetics per treating physician		

Event Name	Diarrhea	
	Management/Next Dose for Oxaliplatin	Management/Next Dose for 5-FU
≤ Grade 1	No change in dose	No change in dose
Grade 2	No change in dose	No change in dose
Recurrent / persistent grade 2	Decrease by 1 dose level	Decrease by 1 dose level
Grade 3	Hold* until < Grade 2. Resume at one dose level lower, if indicated.	Hold* until < Grade 2. Resume at one dose level lower, if indicated. **
Grade 4	Off protocol therapy	Off protocol therapy
*Patients requiring a delay of >2 weeks should go off protocol therapy.		
Recommended management: Loperamide antidiarrheal therapy Dosage schedule: 4 mg at first onset, followed by 2 mg with each loose motion until diarrhea-free for 12 hours (maximum dosage: 16 mg/24 hours) Adjunct anti-diarrheal therapy is permitted and should be recorded when used.		

Event Name	Neutropenia	
	Management/Next Dose for Oxaliplatin	Management/Next Dose for 5-FU
≤ Grade 1	No change in dose	No change in dose
Grade 2	Hold until ≤ Grade 1. Resume at same dose level; consider growth factor with next cycle	Hold until ≤ Grade 1. Resume at same dose level; consider growth factor with next cycle.
Grade 3	Hold* until < Grade 2. Resume at one dose level lower, if indicated; consider growth factor with next cycle especially if dose reduction not done.	Hold* until < Grade 2. Resume at one dose level lower, if indicated; consider growth factor with next cycle especially if dose reduction not done.
Grade 4	Off protocol therapy	Off protocol therapy
*Patients requiring a delay of >2 weeks should go off protocol therapy.		
Consider GM-CSF per recommended doses		

Event Name	Thrombocytopenia
------------	------------------

Grade of Event	Management/Next Dose for [Agent Name]	Management/Next Dose for [Agent Name]
≤ Grade 1	No change in dose	No change in dose
Grade 2	Hold until ≤ Grade 1. Resume at same dose level.	Hold until ≤ Grade 1. Resume at same dose level.
Recurrent Grade 2	Hold until ≤ Grade 1. Decrease by one dose level	Hold until ≤ Grade 1. Decrease by one dose level

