Given the novelty and complexity of this study, a review of the data with the sponsor will occur before initiation of new dose levels. A total of 15 patients will be treated at the MTD (including the 6 from dose escalation phase and an addition 9 patients in expansion cohort) to assess safety of this dose level. Up to 15 patients (including the 6 patients treated at the MTD during dose escalation) will be enrolled into the expansion cohort to further confirm the safety of the MTD (as described in the study primary objective) and to assess efficacy and biomarker change (as described in the study secondary & exploratory objectives). With a total sample size of 15 and assuming the true DLT rate is 0.167, then the probability of observing at least one DLT event is 93.5%. If the true DLT rate is 0.30, then the probability of observing at least one DLT event is 99.5%. The MTD will be deemed to be recommended phase II dose (RP2D) if  $\geq 80\%$  of the patients are able to receive  $\geq 80\%$  of the planned treatment doses. If  $\geq 1/3$  of all patients at this dose experience DLTs, enrollment will be stopped and the Principal Investigator will discuss with all study investigators and with CTEP whether further addition of patients is needed to re-assess the RP2D. Monitoring of all safety and toxicity data is done by the Principal Investigator and the Corresponding Organization on a real-time basis as data are entered into Medidata Rave using the Web Reporting Module.

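### The RP2D feasibility rule counts six escalation patients of whom, on the natural reading, at least five are preselected for completing chemotherapy and radiation

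*Combined protocol and SAP*

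**What the plan says.** Section 5.2 uses two patient sets. For describing toxicity, "All patients who have received at least one dose of the study regimen are evaluable for toxicities". The second set is narrower: "for dose escalation decisions, patients should have completed" at least 80% of the "planned chemotherapy and radiation doses unless the reason for discontinuation is an AE that qualifies for DLT". A DLT is thus the only stated reason for which a non-completer still counts. Talimogene doses are not part of this test.

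The general DLT definition is "DLTs will be defined as clinically significant grade 3 or 4 toxicities possibly or probably related to study treatment", followed by exemptions. One exempts grade 3 diarrhea or vomiting that responds to supportive treatment.

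Section 6.2 has its own rules for ending treatment. In the diarrhea and vomiting tables, the grade 3 hold carries an asterisk to the note "Patients requiring a delay of >2 weeks should go off protocol therapy". For grade 2 oxaliplatin hypersensitivity, the physician may stop oxaliplatin.

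Section 13.1 defines the MTD by at most one DLT in six patients and continues: "A total of 15 patients will be treated at the MTD (including the 6 from dose escalation phase" plus nine more). Under Sections 5.3 and 13.1 the MTD becomes the RP2D if ≥80% "of the patients are able to receive" ≥80% of planned treatment doses. Section 13.4 reports feasibility, as dose intensity, in everyone who started therapy, but does not link that figure to the RP2D decision.

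**The concern.** The RP2D rule is meant to test whether patients can get through the regimen. If six of its 15 patients entered the count partly because they got through chemotherapy and radiation, the test is partly answered before the nine expansion patients are treated.

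The people left out are not a random subset. A patient with exempt grade 3 diarrhea whose treatment is delayed by more than two weeks goes off therapy without a DLT. If that leaves chemotherapy or radiation below 80%, the patient is neither a DLT nor an evaluable non-DLT. Oxaliplatin stopped at discretion for grade 2 hypersensitivity may lead to the same place, depending on whether the 80% is counted per agent, which Section 5.2 does not say. Section 5.5 also allows stopping for an unacceptable adverse event.

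The RP2D is what this trial hands to the next one. A feasibility threshold of 80% that passes too easily at lower completion rates would send forward a regimen that many patients cannot complete.

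**Working it through.** **1. The plan's own figures.** Section 13.1 gives the chance of at least one DLT in 15 patients. The formula is 1 − (1 − p)^15.
- p = 0.167: 1 − 0.833^15 = 0.935. Stated: 93.5%.
- p = 0.30: 1 − 0.70^15 = 0.995. Stated: 99.5%.

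Both reproduce, and both treat the 15 as independent draws from one population. The plan gives no such calculation for the 80%/80% rule.

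**2. Who the six are.** At the MTD at most 1 of 6 has a DLT, so at least 5 are non-DLT patients. Each of those had to reach 80% of chemotherapy and radiation to count. Section 5.1 plans eight FOLFOX doses: 7/8 = 87.5% passes, 6/8 = 75% does not.

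**3. What the nine must deliver.** The rule needs 0.80 × 15 = 12 passes.
- Six preselected: 12 − 6 = 6 of 9 (67%).
- Five preselected, the sixth a DLT patient who did not complete: 12 − 5 = 7 of 9 (78%).

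**4. Chance of meeting the rule.** Let c be the true probability that a patient receives ≥80% of planned doses. The documents give no value, so c is assumed over a range. Binomial tails:

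| c (assumed) | Unselected: P(≥12 of 15) | Five preselected: P(≥7 of 9) | Six preselected: P(≥6 of 9) |
|---|---|---|---|
| 0.60 | 9.1% | 23.2% | 48.3% |
| 0.70 | 29.7% | 46.3% | 73.0% |
| 0.80 | 64.8% | 73.8% | 91.4% |
| 0.90 | 94.4% | 94.7% | 99.2% |

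For c = 0.70 and six preselected, the terms for 6, 7, 8 and 9 passes are 0.267 + 0.267 + 0.156 + 0.040 = 0.730.

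**5. Weighting the two columns.** Assume a 10% DLT rate and 20% stops for toxicity short of a DLT, so c = 0.70, with DLT patients taken as non-completers. Among countable patients the DLT rate is 0.10/0.80 = 0.125. Then P(0 of 6) = 0.875^6 = 0.449 and P(1 of 6) = 6 × 0.125 × 0.875^5 = 0.385, total 0.833. Given that the MTD gate is passed, the weights are 0.449/0.833 = 0.54 and 0.46. The chance of meeting the RP2D rule is 0.54 × 73.0% + 0.46 × 46.3%, about 61%.

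**6. The denominator can decide the verdict.** Suppose eight patients were treated at the MTD level to obtain six countable ones, all six completed, the other two did not, and 6 of 9 expansion patients completed. On 15 patients, 12/15 = 80% and the rule is met. On all 17 starters, 12/17 = 70.6%, against 14 needed (0.80 × 17 = 13.6), and it is not.

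**7. The MTD count.** Under the assumptions of step 5, P(≤1 DLT in 6) is 83.3% when sub-DLT stops are left out. If they were kept as non-DLT patients, p = 0.10 and the figure is 0.9^6 + 6 × 0.1 × 0.9^5 = 88.6%. Leaving them out makes the gate slightly harder to pass.

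**The case against.** The strongest reply is that the selection rests on one reading. Section 5.2 confines the 80% condition to escalation decisions. The RP2D rule speaks of patients treated at the MTD, with no evaluability filter, and Section 13.4 uses everyone who started. If the RP2D denominator is everyone treated at that level, the selection disappears. This stands as an ambiguity, not as an answer: Section 13.1 fixes the group at 15 including six from escalation, and nothing adds uncounted patients back. Section 5.3 attributes the six to expansion; Section 13.1 is explicit that they come from escalation. No replacement rule is stated either. Refilling is an inference from the need for six countable patients.

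Second, no pass is truly assured. The RP2D rule covers planned treatment doses, which include talimogene. Section 6.1 treats a talimogene dose delayed by more than a week as missed, and 3 of 4 is 75%. Counted per agent, an evaluable patient could still fail. This stands and makes the preselected columns upper bounds.

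Third, stops for toxicity short of a DLT may be rare. Section 2.4 reports no DLTs or dose interruptions in the first cohort, although at the lower talimogene level and with the earlier radiation regimen. An investigator might also say that diarrhea forcing a two-week delay had not responded and so was a DLT. Both are fair; at high completion the effect is small.

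Two stronger readings are tempting. A reader might infer that the MTD count is biased toward tolerability. Under the protocol's DLT definition it is not: step 7 shows the opposite direction. A large fall, to 42.0% at the combined rate of 0.30, appears only if every toxicity stop is counted as an event, which is a different endpoint. A reader might also infer that a long grade 2 hold removes patients. The grade 2 neutropenia row says "Resume at same dose level; consider growth factor with next cycle" and, like the grade 2 vomiting and thrombocytopenia holds, has no asterisk tying it to the two-week note. The note names no grade, so the text is unclear, but the point should not rest on it.

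**Conclusion.** The concern holds for the RP2D feasibility rule. As Sections 5.2, 5.3 and 13.1 read together, at least five of the 15 patients meet the chemotherapy and radiation part of the rule by selection. The excess chance of passing is up to 17 percentage points (46% against 30%, before rounding) or 43 points (73% against 30%) at 70% completion, and at most about 5 points at 90%. It is largest below 80% completion, where the rule ought to reject.

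These sizes assume the natural reading of the denominator, independent patients, one common completion rate, and no failures on talimogene among the preselected. The completion rates are assumptions throughout. The documents do not support a conclusion that the MTD determination is tilted toward calling the regimen tolerable. What they leave open there is how a stop for toxicity short of a DLT enters the escalation decision at all.

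**What to change.** In Sections 5.3 and 13.1, state that the 80%/80% RP2D rule is computed on every patient who started therapy at the MTD level, including any who were not evaluable for, or were replaced during, escalation. This matches the all-starters set in Section 13.4. State the replacement rule as well, and check it against the cap of 21 in Section 13.2, since 15 at the MTD level leaves 21 − 15 = 6 places for everyone else.

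Sections 5.2 and 6.2 must be reconciled on how a stop for toxicity short of a DLT enters the escalation decision. Whether such stops count as DLTs is a clinical decision for the sponsor.

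The cost is wording. Section 13.4 already needs dose intensity in all starters, so no new data are required. The downside is that the feasibility figure may look less favourable.
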